1.0 STUDY SYNOPSIS

This study is intended to demonstrate that the ^{13}C -Spirulina Gastric Emptying Breath Test (GEBT) can be successfully administered via a telehealth platform. Telehealth administration of GEBT is where a trained Cairn employee uses a video link to remotely supervise the completion of the test request form, collection of breath samples, cooking and consumption of the test meal and return of breath samples by the patient to Cairn. In the FDA approved method of test administration, these activities are conducted in a clinician's facility, by an appropriately trained healthcare professional (although licensed personnel are not required).

The study will include participants from the intended use population (adults symptomatic for gastroparesis) and subsets of older and less educated participants who may be less familiar with technology, to ensure that the test is suitable for use by the people most likely to be administered the test via telehealth. All study participants will be naïve to GEBT (i.e., have never administered or been administered a GEBT before).

The study will show that there is no increased risk of adverse events when administering GEBT remotely, and that telehealth supervision of the test is adequate to allow proper collection of breath samples, preparation of the test meal, completion of the test request form and return of breath samples to Cairn and is comparable to in-office administration of the GEBT.

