4.0 STUDY GOALS AND OBJECTIVES

The purpose of this study is to establish the usability of a telehealth platform for the administration of GEBT. The objectives of this study are as follows:

- To demonstrate the safety of administering the ¹³C-Spirulina GEBT by telehealth by showing that there is no more than expected frequency of adverse events during administration of GEBT by a telehealth professional, than would be expected during administration of GEBT in a clinician's facility
- To demonstrate patient ability to prepare and administer the ¹³C-Spirulina GEBT, under the supervision of a telehealth professional, according to instructions
- To demonstrate patient ability to complete the GEBT test request form, under the supervision of a telehealth professional, according to instructions
- To demonstrate patient ability to collect GEBT breath samples under the supervision of a telehealth professional
- To demonstrate the ability to successfully ship kits/breath samples to/from home
- To demonstrate the ability of a telehealth platform to function correctly and be used correctly by virtually supervised patients

- **Note:** The steps and order of steps for tele-supervised GEBT administration is the same as that currently conducted in doctors' offices according to approved GEBT labeling.

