5.0 SUBJECT SELECTION

Cairn personnel and their family and friends may volunteer to be a participant in this study provided they are not familiar with the GEBT test administration procedure and have never been administered a GEBT test.

Participants may also be recruited from gastroenterology, multi-disciplinary, primary care or clinical research practices knowledgeable and experienced in the evaluation and treatment of patients suspected of gastroparesis (intended use population for GEBT). Participants should not have previously undergone a gastric emptying breath test.

This study requires a minimum of thirty (30) and up to fifty (50) participants. Of the participants required for this study, at least fifteen (15) must be symptomatic for gastroparesis, at least fifteen (15) must be over the age of 55, and at least fifteen (15) must have no higher than a high school education or equivalent.

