6.4.2 Tasks and Use Scenarios

GEBT is typically administered on a single occasion and subjects administered the test by telehealth would not be expected to become experienced in its use. Therefore, usability testing will be performed where subjects are administered the GEBT via telehealth on a single occasion, and where the subjects have never previously taken a GEBT (in office) and have no prior experience of collecting breath samples.

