6.4.5 Safety of telehealth administration of ^{13}C -Spirulina GEBT

Preliminary risk analysis of the telehealth administration procedure did not identify any increased risks of adverse events associated with telehealth administration of the GEBT compared with in-office administration of the test. This usability study will confirm that there is no more than expected frequency of adverse events during administration of GEBT by a telehealth professional, than would be expected during administration of GEBT in a clinician's facility.

6.4.5.1 Cairn's medical director will review individual adverse events reported during the study to determine whether the adverse events would have been more or less likely to occur during test administration in a physician's office.

6.4.6 Patient ability to prepare and administer the ^{13}C -Spirulina GEBT, under the supervision of a telehealth professional, according to instructions

Ability to prepare GEBT will be assessed by the telehealth administrator's observation of the patient and by a patient questionnaire (Exhibit B) regarding the GEBT that will be completed at the end of the test and returned to Cairn along with the test request form and breath samples.

6.4.6.1 The patient will be asked whether the meal preparation instructions were clear and whether the instructions on meal preparation could be improved upon (Exhibit B).

6.4.6.2 The telehealth administrator will observe and record the following (Exhibit C):

- Was the patient able to transfer the meal to the cooking cup without significant spills?
- Did the patient remove the oxygen absorber?
- Did the patient add the correct amount of water to the meal?
- Did the patient cook the egg for the correct length of time?
- Did the patient flip the egg in the middle of cooking?
- Did the egg appear to be adequately cooked?

6.4.7 Patient ability to complete the GEBT test request form, under the supervision of a telehealth professional, according to instructions

Ability to complete the GEBT test request form will be assessed by Cairn accessioning personnel upon receipt of returned breath samples and by a patient questionnaire (Exhibit B) that will be completed at the end of the GEBT.

6.4.7.1 The patient will be asked whether the test request form was easy to complete (Exhibit B)

6.4.7.2 Accessioning personnel will evaluate the returned test request form and breath samples as follows (Exhibit D).

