6.5.2 Safety of telehealth administration of ^{13}C -Spirulina GEBT

There are no more/more severe adverse events than would have been expected to occur during in-office administration of ^{13}C -Spirulina GEBT.

6.5.3 Patient ability to prepare and administer the ^{13}C -Spirulina GEBT, under the supervision of a telehealth professional, according to instructions

Greater than or equal to 90% of Patient questionnaires record no issues with meal preparation (Exhibit B, Section 4)

Greater than or equal to 90% of meal preparation steps (described in Exhibit C, section 1) were completed successfully.

6.5.4 Patient ability to complete the GEBT test request form, under the supervision of a telehealth professional, according to instructions

Errors in test request forms occur at a rate of ~16% for in-office test administration. There are no more errors in test request form completion than are routinely found in test request forms returned with GEBTs administered in office.

6.5.5 Patient ability to collect GEBT breath samples under the supervision of a telehealth professional

Missing breath samples occur at a rate of ~6% for in-office test administration. There is not a higher incidence of missing breath samples in breath samples collected via telehealth than are routinely found in breath samples returned from GEBTs administered in office.

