14.0 INTENDED USE OF DATA

Data obtained in this study will be used to demonstrate the usability of the ^{13}C -Spirulina GEBT when administered by telehealth procedures and to confirm that the level of risk associated with telehealth administration of ^{13}C -Spirulina GEBT is not greater than that associated with administration of ^{13}C -Spirulina GEBT according to the currently approved labeling.

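### The protocol undertakes to show that telehealth does not raise adverse-event risk, but one arm of 30 to 50 people with no stated in-office rate or margin supports only a description

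*Protocol*

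**What the plan says.** The undertaking appears in five places in the protocol.

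- Section 1.0 (synopsis): "The study will show that there is no increased risk of adverse events when administering GEBT remotely".
- Section 4.0, first objective: safety is to be demonstrated by "showing that there is no more than expected frequency of adverse events during administration of GEBT by a telehealth professional", relative to a clinician's facility.
- Section 6.4.5: the study will confirm the same. Under 6.4.5.1 the sponsor's medical director reviews each reported event to decide "whether the adverse events would have been more or less likely to occur during test administration" in a physician's office.
- Section 6.5.2 (acceptance criterion): "There are no more/more severe adverse events than would have been expected to occur during in-office administration".
- Section 14.0: the data will be used "to confirm that the level of risk associated with telehealth administration of" the test by telehealth is not greater than under the current labelling.

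The design is set elsewhere. Section 5.0: "This study requires a minimum of thirty (30) and up to fifty (50) participants", of whom "at least fifteen (15) must be symptomatic for gastroparesis". Section 6.4.2: "usability testing will be performed where subjects are administered the GEBT via telehealth on a single occasion". There is no in-office arm.

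**The concern.** A statement that risk is not increased is comparative. It needs a comparator, a margin that says how large an increase would matter, and enough people to exclude that increase. The protocol gives none of the three for adverse events.

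The gap stands out because the neighbouring criteria do state in-office benchmarks: about 16% for form errors (6.5.4) and about 6% for missing breath samples (6.5.5). Section 3.5 reports no serious adverse events in the studies and no reportable device events in more than 5,000 tests. Neither is a rate for all adverse events, which is what 6.5.2 judges. Section 11.4 describes a statistical comparison for errors in test procedures and does not mention adverse events.

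At stake is a formal safety conclusion, with a stated use in 14.0, that could be recorded as met after an uneventful small study although the data would be compatible with a higher event rate than in office.

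**Working it through.** **Inputs.** n = 30 to 50 in total and at least 15 symptomatic (section 5.0); one telehealth test per person (6.4.2). The in-office rate for all adverse events, p0, is not stated; 1% to 20% is assumed below. A doubling of p0 is used as an illustrative margin because the protocol sets none. The sample size comes without alpha, power, rate or margin, so there is no planned figure to reproduce. The check is what this size can support.

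**Step 1: the best possible result, no adverse events.** The exact upper limit is 1 − 0.05^(1/n) one-sided 95%, and 1 − 0.025^(1/n) for a two-sided 95% interval.

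| n | One-sided | Two-sided |
|---|---|---|
| 15 (minimum symptomatic subgroup) | 18.1% | 21.8% |
| 30 | 9.5% | 11.6% |
| 50 | 5.8% | 7.1% |

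**Step 2: how easily no events arise.** P(no events) = (1 − p)^n. A true rate of 1% gives none with probability 0.99^30 = 74% or 0.99^50 = 61%. A true rate of 2% gives 0.98^30 = 55% or 0.98^50 = 36%. An event-free study is thus unremarkable at either rate and cannot tell one from the other.

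**Step 3: could the study exclude a doubling?** Let c be the largest count with P(X ≤ c | n, 2·p0) ≤ 0.05, where X is binomial. The chance of excluding a doubling when the risk is truly unchanged is P(X ≤ c | n, p0). The last column is the smallest n at which that chance reaches 80%.

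| Assumed p0 | n = 30 | n = 50 | Smallest n for 80% |
|---|---|---|---|
| 1% | no result suffices | no result suffices | 969 |
| 2% | no result suffices | no result suffices | 452 |
| 5% | c = 0: 22% | c = 1: 28% | 179 |
| 10% | c = 2: 41% | c = 5: 62% | 82 |
| 20% | c = 7: 76% | c = 13: 89% | 36 |

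At 1% and 2%, even zero events fails, because the upper limits in Step 1 (9.5% and 5.8%) lie above the doubled rates of 2% and 4%. Only near 20% does the planned range reach 80%.

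**Step 4: who is counted.** Section 6.6 leaves participants who do not complete all components out of the statistical analysis. If that were applied to adverse events, someone who stopped because of one would be dropped. Any interval should therefore use everyone who starts the test.

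**The case against.** The strongest reply is that this is a usability study, sized by subgroups of 15, with safety as one of six objectives. It is not the only support for safety. Section 6.4.5 cites a preliminary risk analysis that found no added risk. Section 4.0 says the steps and their order match in-office use, 6.4.3 says the kits are the same, and the only study risk listed in 7.2 is allergy to meal ingredients. Case review can also pick up harm specific to the home setting that a crude rate would miss.

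Much of this stands. It makes the confirming language of 6.4.5 and 14.0 less unreasonable than the synopsis wording, and it is a reason to keep the case review. It does not supply a comparator or a margin, and a small usability study can describe adverse events without claiming to have shown that risk is unchanged.

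Four stronger readings are tempting and are not supported:

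- A reader might infer that 6.5.2 can be passed whatever happens. It also bars more severe events, sections 8.2 and 8.3 define intensity and causality scales, and 6.6 allows early termination for the severity or frequency of adverse events.
- A reader might attach a probability to a doubled risk passing 6.5.2. That requires a counting rule, such as observed no higher than expected, which the protocol does not contain.
- A reader might say that 30 to 50 people can never exclude an increase. That depends on the unstated rate, as the 20% row shows.
- A reader might treat the missing rate as a defect in itself. A statistical analysis plan that is not shown could give a rate or an interval method. The point rests on the claim and the criterion, which the protocol itself fixes.

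**Conclusion.** The point holds: sections 1.0, 4.0, 6.4.5, 6.5.2 and 14.0 claim a property the design does not have. The upper limits of 9.5% (n = 30) and 5.8% (n = 50) after zero events, 11.6% and 7.1% two-sided, need no assumption about the in-office rate.

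That an increase cannot be reliably excluded rests on the assumed range for that rate and on a doubling as the illustrative margin. With in-office rates of 10% or below, the chance of excluding a doubling stays under 80% throughout the table; at about 20% it is 76% at 30 participants and 89% at 50. Section 3.5 describes an excellent safety profile and gives no support for so high a rate. Without a margin, no sample in the planned range can exclude every increase. The flaw is in the stated conclusion and criterion. Running a small usability study is not itself at fault.

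**What to change.** In sections 1.0, 4.0, 6.4.5 and 14.0, replace the undertaking to show or confirm no increased risk with this: adverse events will be described among all participants who start the test, with the exact 95% confidence interval for the proportion with an adverse event and the largest rate not excluded.

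Make 6.5.2 descriptive in the same way. Report the interval beside the in-office adverse-event rate and its source, both fixed before the first test, together with the medical director's review of setting-specific events. Do not conclude that risk is not increased. Setting the interval against the in-office rate as a pass rule would not work: if the upper limit had to lie at or below a rate of 1% to 5%, even zero events in 50 people (5.8%) would fail.

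The cost is protocol wording and one exact interval. The safety claim becomes less favourable. No extra participants or staff are needed.

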6.4.9 Ability to successfully ship kits/breath samples to/from home

Ability to ship GEBT kits/breath samples to/from home will be assessed by surveying patients regarding shipping (Exhibit B) and by recording the dates that kits were shipped and received.

6.4.9.1 Patients will be asked whether they have any problems receiving their GEBT kit (Exhibit B)

6.4.9.2 Patients will be asked whether they had any issues returning breath samples to Cairn (Exhibit B)

6.4.9.3 Cairn personnel will record dates when each kit and breath samples are shipped/received.

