6.5.6 Ability to successfully ship kits/breath samples to/from home

Kits are delivered/received by subjects in time for the scheduled breath test and breath samples and test request form are returned to Cairn/analyzed within the 28-day stability period of breath samples.

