11.4 Statistical Analysis

Comparisons of rates of occurrence of errors in test administration procedures between telehealth and in-office administered tests will be performed according to accepted statistical techniques.

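### The comparability conclusion in section 1.0 goes further than the acceptance criteria for meal preparation and return timing, which show only that absolute limits were met

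*Protocol*

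**What the plan says.** The synopsis (1.0) states what the study will show. It says that "telehealth supervision of the test is adequate to allow proper collection of breath samples, preparation of the test meal", then adds completion of the test request form and "return of breath samples to Cairn and is comparable to in-office administration of the GEBT". Section 11.4 plans "Comparisons of rates of occurrence of errors in test administration procedures between telehealth and in-office administered tests", using accepted techniques; it does not list the procedures.

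The acceptance criteria in 6.5 are of two kinds.

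- **With an in-office reference.** Adverse events must be no more frequent or severe than expected in office (6.5.2, no rate given). For forms, "Errors in test request forms occur at a rate of ~16% for in-office test administration", and telehealth must not exceed the routine error level (6.5.4). Missing breath samples are set against an in-office rate of about 6% (6.5.5).
- **With an absolute limit only.** Meal preparation (6.5.3) has two requirements: at least 90% of patient questionnaires free of meal-preparation issues, and "Greater than or equal to 90% of meal preparation steps (described in Exhibit C, section 1) were completed successfully". For shipping (6.5.6), kits must arrive in time and "breath samples and test request form are returned to Cairn/analyzed within the 28-day stability period of breath samples".

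Section 5.0 asks for 30 to 50 participants. Under 6.1 all of them are tested by telehealth, and no in-office arm is described.

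**The concern.** A conclusion of comparability needs something to compare with. For meal preparation and for the timing of sample return, the protocol provides neither a concurrent in-office group nor an in-office rate. A pass on 6.5.3 and 6.5.6 therefore carries no information about how telehealth stands relative to in-office practice on these two outcomes.

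Meal preparation is where the gap matters most. According to 1.0, the activities under the approved method are conducted in the clinician's facility by a trained healthcare professional. Under telehealth, a participant with no prior training (6.4.4) cooks the meal at home under video supervision. Performance could plausibly differ, and the plan does not measure whether it does.

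At stake is the wording of the conclusion. If every criterion is met, 1.0 lets a report describe telehealth administration as comparable to in-office administration without saying that, for these outcomes, only adequacy was tested.

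**Working it through.** **1. Each outcome against its reference**

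| Outcome | Criterion | In-office reference |
|---|---|---|
| Adverse events | 6.5.2: not more, or more severe, than expected in office | Yes, qualitative (medical director's review, 6.4.5.1) |
| Test request form errors | 6.5.4: no more than routine in-office level | Yes, about 16% |
| Missing breath samples | 6.5.5: incidence not higher than in office | Yes, about 6% |
| Meal preparation | 6.5.3: at least 90% of questionnaires and at least 90% of steps | None |
| Timeliness of sample return | 6.5.6: within the 28-day stability period | None |

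The data collected for the last two rows come from telehealth sessions. Exhibit C is completed by the telehealth administrator about the participant. For shipping, 6.4.9 plans a patient survey and says "Cairn personnel will record dates when each kit and breath samples are shipped/received". Neither yields an in-office rate.

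The protocol states no margin, power or error level for these outcomes, so there is no planned figure to reproduce.

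**2. What the steps requirement in 6.5.3 tolerates**

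Inputs: six steps (Exhibit C, section 1), 30 to 50 participants (5.0), limit 90% (6.5.3). Steps are treated as independent. If steps fail together within a participant, the intervals would be wider.

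- 30 participants: 6 × 30 = 180 steps; 10% of 180 = 18 failures allowed. Exact (Clopper–Pearson) 95% interval for 18/180: 6.0% to 15.3%.
- 50 participants: 6 × 50 = 300 steps; 10% of 300 = 30 failures allowed. Exact 95% interval for 30/300: 6.8% to 14.0%.

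Binomial probability of meeting the steps requirement:

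| True step-failure rate | 180 steps (at most 18 failures) | 300 steps (at most 30 failures) |
|---|---|---|
| 5% | 0.998 | 1.000 |
| 8% | 0.869 | 0.913 |
| 10% | 0.562 | 0.548 |
| 12% | 0.243 | 0.164 |

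These figures describe the steps requirement alone. 6.5.3 also needs the questionnaire result, at least 27 of 30 or 45 of 50. The joint probability cannot be computed without knowing how the two measures are related. (The questionnaire requirement cites Exhibit B, Section 4; in the exhibit, meal preparation is section 5 and section 4 is breath sample collection. That reference should be corrected, but it does not affect this point.)

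**3. Distance from in-office performance**

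Gap at the pass line = in-office step success − 90%. The first term is not in the protocol. Over an assumed range:

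- 90% in office: 90 − 90 = 0 points
- 95% in office: 95 − 90 = 5 points worse
- 99% in office: 99 − 90 = 9 points worse

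The same pass fits anything from no difference to a 9-point deficit, depending wholly on the assumption. For return timing no gap can be computed at all.

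**The case against.** The sponsor could fairly answer on five grounds.

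- **Grammar of the synopsis.** The four tasks are governed by the statement about adequacy; comparability describes supervision as a whole. A reader might infer that 1.0 promises comparability task by task. The text does not say that, and 6.5.3 and 6.5.6 are suitable criteria for adequacy. This stands. What remains is that 1.0 defines telehealth administration through these same tasks and puts no limit on the overall claim.
- **Other sections are more careful.** Section 4.0 frames meal preparation and shipping as abilities to be demonstrated, and 14.0 limits the use of the data to usability and level of risk. This stands, and it confines the correction to 1.0 and 11.4.
- **Sample return is partly referenced.** The missing-sample benchmark in 6.5.5 concerns samples returned from in-office tests, and 6.4.7.2 counts presence of the form in the mailer among the form checks. A reader might infer that half of the listed tasks have no comparator. That overstates it: for return, the gap is in timing.
- **An absolute limit is reasonable for a usability study.** Agreed. In-office preparation by a professional need not offer a matching rate of patient success. The point asks for no comparator, only for a conclusion that fits the criteria.
- **A statistical analysis plan may define the comparisons in 11.4.** It may, and the lack of detail there is not a defect. But the pass rules are fixed in 6.5, and for these two outcomes they are absolute.

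**Conclusion.** The point holds in a limited form. Comparability with in-office administration can be concluded, at most, for adverse events, form errors and missing breath samples. For meal preparation and return timing, meeting the criteria shows adequacy only. Meal preparation is the more important of the two.

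The tolerance of 18 of 180 or 30 of 300 failed steps gives the scale of the steps requirement. It rests on independence between steps and does not by itself amount to a pass on 6.5.3.

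A reader might infer that a home procedure clearly worse than in-office practice would pass and be called comparable. The documents do not support that: they contain no in-office step-failure rate, and the 0 to 9 point range follows only from the assumed 90% to 99% in-office success. Size and direction of any difference are unknown.

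The study can run as designed. What needs to change is the stated conclusion.

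**What to change.** - **Section 1.0:** limit the comparability conclusion to adverse events, test request form errors and missing breath samples. State that meal preparation and timeliness of sample return are shown only to meet the limits in 6.5.3 and 6.5.6.
- **Section 11.4:** limit the telehealth versus in-office comparison of procedural error rates to form errors and missing breath samples. Adverse events stay with the qualitative judgement in 6.5.2.
- **Sections 6.5.3 and 6.5.6:** if the sponsor already holds in-office figures for meal preparation or return timing, state them there with their source and compare against them. Otherwise draw no comparability conclusion for these outcomes.

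The cost is the rewording of two sections and a slightly narrower conclusion. No participants, procedures or criteria need to be added.
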